7.2 Secondary Analyses

The Secondary endpoints will include the following:

- Time from randomization to each component of the primary endpoint:
 - All-cause mortality
 - Any stroke (ischemic and hemorrhagic)
 - Any occurrence of major or life-threatening bleeding (as per VARC2 definition of bleeding)
- Time to death from cardiovascular causes
- Time to ischemic stroke
- Time to hemorrhagic stroke
- Arterial or venous thrombosis or embolism
- Rehospitalization related to WATCHMAN procedure or WATCHMAN device.

Analysis of time-to-event endpoints for the components will be analyzed similarly to that of the primary endpoint, except there will be no testing of the non-inferiority hypothesis. Point estimates and 95% confidence intervals will be derived from a Cox proportional model with treatment group as a factor. Descriptive frequencies of the endpoints and Kaplan-Meier curves will be presented. P-values may be

provided for descriptive purposes, but should not be considered informative. The frequency of procedure related complications, device/implant failure or systemic embolism will be summarized with descriptive statistics.

KCCQ-12 score quality of life (QoL) subdomains at baseline and follow-up visits will be summarized with descriptive statistics. Change from baseline in KCCQ-12 will be analyzed using the mixed model for repeated measures (MMRM). The model will include treatment group, baseline value, visit, visit and treatment interaction. Subject will be treated as the random effect, and variance covariance component will be compound symmetry.

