3.3 SECONDARY ENDPOINTS

All-cause mortality, stroke (ischemic and hemorrhagic), bleeding (major and/or life-threatening as per VARC2 definitions), cardiovascular mortality, arterial or venous thrombosis or embolism, rehospitalization related to the WATCHMAN procedure or device, QoL (KCCQ-12) at follow-up, and procedural costs related to the initial TAVR and WATCHMAN procedures.

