7.2 ADVERSE EVENT REPORTING

An adverse event is an untoward event that affects the patient's health or safety. When reporting an adverse event, the investigator will complete the AE report form.

Adverse experiences that require reporting include any adverse event with clinical symptoms that could possibly be contributed to any of the following:

- The WATCHMAN device
- The TAVR device
- The WATCHMAN implant procedure (including pericardial effusion, device embolism, stroke)
- The TAVR implant procedure (including pericardial effusion, device embolism, stroke)
- Any study required procedures (i.e., clinical complications from protocol required TEE, etc.)

The following adverse events will also be reported regardless of relationship to the device(s) or procedure(s):

- Any event with an outcome of death
- Stroke (ischemic and/or hemorrhagic) and TIA
- Any events associated with bleeding
- Arterial or venous thrombosis or embolism
- Rehospitalization related to procedure or device implantation
- Any potential Unanticipated Adverse Device Effects (see definition below)

Each adverse event will be evaluated by the investigator for relatedness and seriousness.

i) Relatedness

The relatedness of an adverse event to the study, WATCHMAN Device, TAVR device, WATCHMAN procedures or TAVR procedure will be assessed by the Investigator for each submitted adverse event form.

- **Device Related:** An adverse event that results from the presence or performance of the device or any other component of the system.

- **Procedure Related:** An adverse event that occurs due to the system implantation procedure. Adverse events that are contributable to the anesthesia or contrast media given during the implant procedure will be considered procedure related.
- **Unknown:** An adverse event that cannot be determined to have a causal relationship with either the system or procedure will be classified as unknown.
- **Not Related:** An adverse event that is determined to not have a causal relationship with either the system or procedure.

ii) Seriousness

Adverse events as described above will be evaluated for serious injury. Adverse events resulting in death or serious injury are to be reported to the sponsor within 24 hours of learning of the event. Serious injury is an injury or illness that:

- Is life-threatening, or
- Results in permanent impairment of a body function or permanent damage to a body structure, or

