9.4 DESCRIPTION OF STATISTICAL METHODS

9.4.1 GENERAL APPROACH

The ITT population will be used to analyze the primary and secondary endpoints. The non-inferiority hypothesis will only be tested using the primary endpoint of all-cause mortality, stroke, and major/life-threatening bleeding. Event rates, hazard ratio and 95% confidence intervals and a p-value associated with the non-inferiority hypothesis will be provided. If the non-inferiority objective is met, a p-value for the superiority hypothesis will also be provided. Secondary endpoints will be summarized using event rates, hazard ratios and 95% confidence intervals. Nominal p-values for comparisons between treatment groups will be provided for descriptive purposes only.

All patients should be followed until the termination of the study, regardless of adherence to the treatment strategy. Available information on patients lost to follow-up will be included in the analyses. Patients not reaching a primary endpoint by the time of study termination will be censored at their last known assessment.

Statistical methods will be further outlined in the Statistical Analysis Plan (SAP).

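### A control patient can have WATCHMAN-related rehospitalization only after an off-assignment implant, so the hazard ratio planned for secondary endpoints is non-estimable or uninformative here

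*SAP*

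**What the plan says.** **Definition.** Every listing of the endpoint ties it to one device. Protocol 3.3 has "rehospitalization related to the WATCHMAN procedure or device" and SAP 7.2 has "Rehospitalization related to WATCHMAN procedure or WATCHMAN device"; the Protocol Summary, Protocol 9.4.3 and SAP 2.2.2 agree.

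**Planned summary.** Protocol 9.4.1 says: "Secondary endpoints will be summarized using event rates, hazard ratios and 95% confidence intervals". It adds nominal p-values for comparing the arms, as description only, and names no exception.

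**SAP method.** SAP 7.2 says "Analysis of time-to-event endpoints for the components will be analyzed similarly to that of the primary endpoint", without testing non-inferiority, and then "Point estimates and 95% confidence intervals will be derived from a Cox proportional model with treatment group as a factor". It also says "Descriptive frequencies of the endpoints and Kaplan-Meier curves will be presented". P-values may be "provided for descriptive purposes, but should not be considered informative". The rehospitalization item carries no *time to* label, unlike the mortality, stroke and bleeding items.

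**Crossover.** Protocol 3.1 asks sites to avoid WATCHMAN in the TAVR-only arm during the first year unless medically necessary, and states no restriction for the second year. Under SAP 5.2 such a patient stays in the control arm for the intention-to-treat analysis, to 730 days.

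**Collection.** Protocol 7.2 lists among reportable events "Rehospitalization related to procedure or device implantation". That line does not name a device, but the section covers both the TAVR and the WATCHMAN device and procedure, and the investigator assesses relatedness to each.

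**The concern.** A between-arm hazard ratio is meaningful only if patients in both arms can have the event under the treatment they were assigned. Here assignment to TAVR alone removes the exposure that defines the event. A readmission for a TAVR complication counts in neither arm, while a readmission for a WATCHMAN complication counts almost exclusively in one. The comparison can then realistically point only against the device, whatever the combined procedure does to procedure- or device-related readmission overall.

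At stake is one line of the secondary results table: an infinite or very large hazard ratio, possibly with a small nominal p-value, that follows from the definition. If this is found only at analysis, a substitute endpoint would be chosen after the data are seen.

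**Working it through.** **1. The plan's own figure.** The documents give no figure for this endpoint. Their event target for the primary endpoint reproduces: 4 × (1.960 + 0.842)² / (ln 1.5)² = 31.40 / 0.1644 = 191. Nothing below affects it.

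**2. Inputs.** From the documents: 175 patients per arm, 10% dropout per year (Protocol 9.4.4, SAP 4) and follow-up to 730 days (SAP 5.2). Assumed, because the documents give neither:
- c, the share of control patients who receive a WATCHMAN: 2% to 10%
- q, the proportion of implanted patients with a WATCHMAN-related rehospitalization: 3% to 10%

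**3. No control events.** With n₁ device-arm and n₀ control patients at risk, each device-arm event adds −ln(n₁ + n₀e^(−β)) to the Cox log partial likelihood. This rises with β at every event, towards −ln n₁, so there is no maximum. One simulated data set (175 per arm, 2 years, 10% yearly dropout, 4 v 0 events) shows it:

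| β | log partial likelihood |
|---|---|
| 0 | −22.91 |
| 2 | −20.63 |
| 5 | −20.15 |
| 10 | −20.1230 |
| 20 and 40 | −20.1228 |

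The estimate diverges and there is no upper limit.

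**4. Exact interval.** For k v 0 events and similar exposure, the lower 95% limit of the rate ratio is p/(1 − p) with p = 0.025^(1/k). The upper limit is infinite.
- k = 5: p = 0.478, lower limit 0.92
- k = 9: p = 0.664, lower limit 1.97
- k = 17: p = 0.805, lower limit 4.13

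These k are close to the expected device-arm counts, 175 × q = 5.25, 8.75 and 17.5 for q = 3%, 5% and 10%.

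**5. Nominal p-value.** As an illustration (neither document plans this test), the two-sided exact p for k v 0 is 2 × (1/2)^k. Five events give 0.0625 and six give 0.031. Six WATCHMAN-related readmissions in 175 patients would fall below 0.05 through the definition alone.

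**6. Some crossover.** Expected control events are 175cq, expected device-arm events are 175q, and P(no control event) = (1 − cq)^175. The ratio of expected counts is 175q / 175cq = 1/c.

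| c | q | Expected control | Expected device arm | P(no control event) | 1/c |
|---|---|---|---|---|---|
| 2% | 3% | 0.105 | 5.25 | 0.90 | 50 |
| 2% | 10% | 0.35 | 17.5 | 0.70 | 50 |
| 5% | 5% | 0.44 | 8.75 | 0.65 | 20 |
| 10% | 3% | 0.53 | 5.25 | 0.59 | 10 |
| 10% | 10% | 1.75 | 17.5 | 0.17 | 10 |

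q cancels from the ratio. A finite hazard ratio would therefore mainly describe how many controls crossed over. The calculation takes the same q for crossover implants as for assigned ones, assumes that every device-arm patient is implanted, and gives crossover patients full time at risk. Later crossover would raise the ratio further.

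**The case against.** The strongest reply is that the SAP may already intend a purely descriptive report. The Cox sentence in SAP 7.2 concerns time-to-event endpoints for the components, and this item is neither labelled time-to-event nor a component of the primary endpoint. The section also plans frequencies. The sentence in Protocol 9.4.1 is generic: it cannot apply literally to quality of life or procedural costs, which are also secondary endpoints, and that section defers detail to the SAP. A device-specific safety count is a legitimate thing to report.

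Much of this stands. A reader might infer that SAP 7.2 commits to a Cox hazard ratio here; its text does not clearly do so. But it does not exempt the item from the protocol's rule or name another method. The missing label is not decisive, since arterial or venous thrombosis or embolism also lacks one.

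Three other stronger readings are tempting:

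- *Controls cannot have the event, so the hazard ratio is certainly undefined.* Protocol 3.1 allows WATCHMAN in controls when medically necessary and states no second-year restriction. Under the assumed ranges the chance of no control event runs from 0.90 down to 0.17.
- *The endpoint defeats the trial's single-hospitalization rationale.* Protocol 1.2 contrasts one combined procedure with two separate ones. The control arm is TAVR plus medical therapy, so no rehospitalization endpoint in this trial could test that.
- *Bleeding on medical therapy is ignored.* Major and life-threatening bleeding counts in both arms through the primary endpoint and its components. Only the readmission goes uncounted.

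**Conclusion.** The point holds in limited form. The event is open to one arm by assignment and to the other only through crossover, and the protocol's general rule for secondary endpoints yields a hazard ratio that is non-estimable without control events and otherwise mainly reflects the crossover rate (about 50 to 10 for assumed crossover of 2% to 10%). The divergence and the 1/c relation follow from the definition; the sizes rest on assumed c and q.

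The consequence is modest. The endpoint is secondary, no hypothesis is tested on it, and both documents call the p-values descriptive. The primary analysis, the 191 events and the sample size of 350 are untouched. The change should still be made before analysis, because it costs little and avoids a misleading line in the results.

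**What to change.** In SAP 7.2 and Protocol 9.4.1 and 9.4.3:

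1. Keep WATCHMAN-related rehospitalization as a device-arm safety result, reported as a count and rate or a cumulative incidence. List separately any such event in control patients who received the device. State that no hazard ratio or p-value will be given.
2. For any between-arm comparison, add rehospitalization related to the index procedure or any implanted device (TAVR or WATCHMAN), and name its method.

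The cost is wording in two documents. New data collection should not be needed, because the Protocol 7.2 reporting list appears to capture these readmissions in both arms. The case report form is not among the documents, so the sponsor should confirm that.

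The two-arm definition has two limits worth stating in the SAP. The device arm still has one more procedure and one more implant at risk. Readmission for bleeding on medical therapy is not necessarily captured, although the bleeding itself is reported.

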9.4.4 SAMPLE SIZE

The WATCH-TAVR is a randomized, prospective multi-center event-driven non-inferiority study to determine the safety and efficacy of the WATCHMAN device in patients with non-valvular AF undergoing TAVR for aortic stenosis. The control group consists of patients undergoing TAVR who are on standard medical practice, with oral anticoagulation at the discretion of the treating physician. The treatment group will have the WATCHMAN implantation procedure performed simultaneously with TAVR. The primary endpoint is a composite of all-cause mortality, stroke, life-threatening or major bleeding. The objective of the study is to demonstrate non-inferiority of the TAVR plus WATCHMAN device compared to the TAVR only group.

Data from the PARTNER¹ trial, along with the SOURCE-XT¹⁰ and FRANCE-2¹¹ registries show all-cause mortality rates in TAVR patients with AF vary from 19-30%, stroke rates from 6-10% and major/life-threatening bleeding from 17-22%. The PROTECT-AF trial for the WATCHMAN device in non-valvular atrial fibrillation patients reported a risk reduction of nearly 40% for the primary composite endpoint of stroke, systemic embolization or cardiovascular or unexplained death (RR 0.61, 95%CrI 0.42-1.07)⁴.

The following assumptions were used to determine the sample size needed to assess the non-inferiority hypothesis for the composite primary endpoint of all-cause mortality, stroke or major or life-threatening bleeding:

- One-sided $\alpha = 0.025$
- Primary event rate in the control population (TAVR only) of 35% at one year
- Non-inferiority margin of 1.5
- Underlying hazard ratio of active to control is 1.0
- Power at least 80%
- Lost to follow-up rate 10%

Assuming level of significance (α) to be 0.05 (or $\alpha = 0.025$ one-sided) and aiming for a study power ($1 - \beta$) of 80%, we estimate 191 primary events will be needed to rule out an upper limit of the one-sided 97.5% confidence interval of 1.5. Assuming an enrollment duration of 18 months, follow-up period of 24 months, and 10% drop out rate per annum, the minimum total sample size required is 350 (175 per group).

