2.2.2 Secondary endpoints

1. Time from randomization to each component of the primary endpoint: all-cause mortality, any stroke and any occurrence of major or life-threatening bleeding (as per VARC2 definition of bleeding).
2. Time to death from cardiovascular causes
3. Time to ischemic stroke
4. Time to hemorrhagic stroke
5. Arterial or venous thrombosis or embolism
6. Rehospitalization related to WATCHMAN procedure or WATCHMAN device.

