4 SAMPLE SIZE

This randomized control trial will aim to prospectively enroll 350 patients having non-valvular AF undergoing standard care of TAVR. The control group consists of patients undergoing TAVR who are on standard medical practice, with oral anticoagulation at the discretion of the treating physician. The treatment group will have the WATCHMAN implantation procedure performed simultaneously with TAVR. The primary endpoint is a composite of all-cause mortality, stroke, life-threatening or major bleeding. The objective of the study is to demonstrate non-inferiority of the TAVR plus WATCHMAN device compared to the TAVR only group.

The following assumptions were used to determine the sample size needed to assess the non-inferiority hypothesis for the composite primary endpoint of all-cause mortality, stroke or major or life-threatening bleeding:

- One-sided $\alpha = 0.025$
- Primary event rate in the control population (TAVR only) of 35% at one year
- Non-inferiority margin of 1.5
- Underlying hazard ratio of active to control is 1.0
- Power at least 80%
- Lost to follow-up rate 10%

Assuming level of significance (α) to be 0.05 (or $\alpha = 0.025$ one-sided) and aiming for a study power ($1 - \beta$) of 80%, we estimate 191 primary events will be needed to rule out an upper limit of the one-sided 97.5%

confidence interval of 1.5. Assuming an enrollment duration of 18 months, follow-up period of 24 months, and 10% drop out rate per annum, the minimum total sample size required is 350 (175 per group).

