5.4.2 Durations

- Time to Event (e.g. time to primary endpoint) will be calculated as (event date/time – randomization date/time). Patients not having an event, or lost to follow-up will be censored at the minimum of the time of their last documented follow-up date, death date, or 2 years (730 days).
- Other durations of time will be calculated similarly as (date/time of interest – reference date/time +1)

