7 ANALYSES

7.1 Primary Analysis

The ITT analysis will include all positively adjudicated post-randomization primary endpoints within the ITT analysis set through 24 months (730 days) after randomization.

The study is designed to demonstrate the non-inferiority of the WATCHMAN device compared to the control group, with regards to the primary endpoint (composite of all-cause mortality, stroke (ischemic and hemorrhagic), or bleeding (major and/or life-threatening)). Non-inferiority will be assessed using the 1-sided 97.5% confidence interval around the hazard ratio (WATCHMAN-TAVR: TAVR only). Non-inferiority will be demonstrated if the 1-sided 97.5% upper confidence limit for the difference in proportions is less than 1.5. If the non-inferiority objective is met, additional analyses to assess superiority of the WATCHMAN group to the control group will be performed. The composite primary endpoint will also be summarized as events per 100 patient-years of follow-up.

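### Kaplan-Meier curves that censor deaths will overstate the absolute risks of stroke, bleeding and cardiovascular death; cumulative incidence curves should be planned instead

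*SAP*

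**What the plan says.** SAP 7.2 lists as secondary endpoints the time to each component of the composite (all-cause mortality, any stroke, major or life-threatening bleeding) and the time to cardiovascular death, ischemic stroke and hemorrhagic stroke. On method it says "Analysis of time-to-event endpoints for the components will be analyzed similarly to that of the primary endpoint", without the non-inferiority test. Estimates come from a Cox model with treatment as the only factor. On presentation it says "Descriptive frequencies of the endpoints and Kaplan-Meier curves will be presented". Protocol 9.4.3 carries the same text.

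The censoring rule is in SAP 5.4.2. Patients who have no event or are lost to follow-up "will be censored at the minimum of the time of their last documented follow-up date, death date, or 2 years (730 days".

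Two further statements bear on absolute risk. Protocol 9.4.1 says "Secondary endpoints will be summarized using event rates, hazard ratios and 95% confidence intervals", without defining the event rate. SAP 7.1 says "The composite primary endpoint will also be summarized as events per 100 patient-years of follow-up", but promises this for the composite only.

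Neither document mentions cumulative incidence or any other competing-risk method.

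**The concern.** A patient who has died cannot later have a stroke or a bleed. Kaplan-Meier treats that patient as someone who left observation and still carries the same future risk as the survivors. One minus the curve then describes a world in which nobody dies first, and it lies above the proportion of patients who actually have the event. The same holds for cardiovascular death when other deaths are censored.

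Stroke and bleeding are what the device is meant to prevent, so readers will look for their absolute risk by arm. No planned output gives it directly:

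- The curves err high.
- Crude frequencies err low when patients drop out.
- A rate per 100 patient-years, even if extended to the components, is not a cumulative risk.

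Mortality in this population is substantial by the protocol's own account, so the competing event is not rare.

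**Working it through.** The plan gives no figure for this difference, so there is none to reproduce.

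**Inputs**

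- Protocol 9.4.4 cites "all-cause mortality rates in TAVR patients with AF vary from 19-30%, stroke rates from 6-10% and major/life-threatening bleeding from 17-22" per cent, with no time horizon.
- SAP 4 assumes "Primary event rate in the control population (TAVR only) of 35% at one year", 10% dropout per annum and 175 patients per arm.
- Follow-up ends at 730 days (SAP 5.2).

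**Formulas**, with constant event hazard he, constant death hazard hd and T = 2 years:

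- Cumulative incidence (CIF) = he/(he+hd) × [1 − exp(−2(he+hd))]
- One minus Kaplan-Meier = 1 − exp(−2he)

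**(a) Cited rates read as two-year risks.** Take 30% mortality and 22% bleeding. Then hd = −ln(0.70)/2 = 0.1783, and solving CIF = 0.22 gives he = 0.1500. Check: 0.1500/0.3283 × [1 − exp(−0.6566)] = 0.220. One minus Kaplan-Meier is 1 − exp(−0.300) = 25.9%, which is 3.9 points too high.

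| Mortality | Event | CIF | 1 − KM | Excess (points) | Relative excess |
|---|---|---|---|---|---|
| 19% | stroke | 6% | 6.6% | 0.6 | 10.8% |
| 19% | stroke | 10% | 11.1% | 1.1 | 10.7% |
| 19% | bleeding | 17% | 18.8% | 1.8 | 10.5% |
| 19% | bleeding | 22% | 24.3% | 2.3 | 10.4% |
| 30% | stroke | 6% | 7.1% | 1.1 | 18.6% |
| 30% | stroke | 10% | 11.8% | 1.8 | 18.4% |
| 30% | bleeding | 17% | 20.1% | 3.1 | 18.1% |
| 30% | bleeding | 22% | 25.9% | 3.9 | 17.8% |

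**(b) Cited rates read as one-year risks.** All hazards are scaled so that death, stroke and bleeding together equal −ln(0.65), which matches the 35% composite. Over the eight combinations of the cited limits, the two-year excess is 1.5-2.6 points for stroke (15.2-24.8%) and 4.1-5.2 points for bleeding (14.6-23.9%). Without the scaling, the excess is 20-39%: 2.3-6.1 points for stroke and 5.9-11.7 for bleeding.

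**Sensitivity to timing (assumptions)**

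- If 75% of the first-year event hazard falls in the first 30 days and death does not cluster, the excess is 4.3-7.6% under (a) and about 6-11% under (b). In points this is 0.3-0.8 for stroke and 0.7-1.6 for bleeding.
- If deaths are equally early, (a) returns to 10-19%.
- If mortality triples after an event, with total mortality held fixed, (a) becomes 8-18%.

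**Cardiovascular death.** Let a share s of deaths be cardiovascular (assumed 40-70%) and h be the total death hazard. CIF = s[1 − exp(−2h)] and 1 − KM = 1 − exp(−2sh). The excess is 3-11% under (a) and 4-14% under (b).

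**Crude frequencies.** Adding a dropout hazard of −ln(0.9) = 0.105 per year puts the crude proportion about 9% below the CIF with constant hazards, and 3-4% below with early events.

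**Person-time.** In the worked example the rate is 15.0 per 100 patient-years. Converting it gives 1 − exp(−0.30) = 25.9% again, not 22.0%.

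**Scale.** The 95% half-width, 1.96 × √(p(1−p)/175), is 3.5 and 4.4 points at 6% and 10%, and 5.6 and 6.1 points at 17% and 22%.

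**The case against.** The strongest reply is that nothing inferential is wrong. The composite contains death, the Cox hazard ratios are valid as cause-specific ratios, secondary p-values are descriptive, and no two-year Kaplan-Meier estimate is promised. The error arises only when someone reads a risk off a curve. All of this stands, and it limits the importance of the point.

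The comparison between arms is also little affected when mortality is similar. With equal mortality and an assumed hazard ratio of 0.7, the two-year risk ratio is 0.712-0.729 by cumulative incidence and 0.712-0.731 by one minus Kaplan-Meier. The risk difference moves more: from 2.9 to 3.2 points (10% control risk, 19% mortality) and from 6.0 to 7.0 (22% and 30%). If mortality differs by arm, the inflation differs too.

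The size may be smaller than shown. The trial excludes patients with a life expectancy under two years, so its mortality may be below the cited range. The assumption list in the sample-size section gives 10% loss to follow-up without a period. If that is a total, a dropout hazard of 0.053 per year leaves the crude frequencies only about 5% low under (a). The excess is also mostly within sampling error, although the unscaled version of (b) can exceed it for bleeding. A bias in one direction does not shrink with sample size, and a confidence interval does not correct it.

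Finally, the analysis paragraph opens with the components, so a narrow reading would leave cardiovascular death without a curve. The sentence on curves speaks of the endpoints generally, and stroke and bleeding are covered on either reading.

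**Conclusion.** The concern holds. The plan states the censoring rule and the estimator, and together they give curves whose complement is too high whenever some deaths precede the event. The relative excess at two years is about 10-25% under constant hazards, in readings (a) and scaled (b). It is roughly 4-11% if events are early and deaths are not, and up to 39% if the cited rates are one-year risks taken without scaling. These figures rest on the protocol's cited rates, an unstated time horizon and assumed hazard shapes; the direction does not depend on them.

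"Arterial or venous thrombosis or embolism" and WATCHMAN-related rehospitalization are not worded as times to event, so the point reaches them only if curves are drawn. The primary conclusion is untouched. This is a cheap improvement to the reporting of the outcomes that the device targets.

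**What to change.** - **SAP 7.2:** present Aalen-Johansen cumulative incidence curves, with two-year estimates and 95% confidence intervals by arm, for any stroke, ischemic stroke, hemorrhagic stroke, major or life-threatening bleeding, and cardiovascular death.
- **SAP 5.4.2:** state that for these curves death is a competing event (non-cardiovascular death in the case of cardiovascular death). The Cox models continue to censor at death and are labelled cause-specific.
- **Thromboembolism and WATCHMAN-related rehospitalization:** state whether curves will be drawn and, if so, use the same method.
- **Kaplan-Meier curves:** these may stay as a supplement.

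The cost is a short wording change and a little programming. Event and death dates are already collected, and cause of death is already needed for the cardiovascular death endpoint. Reported component risks will be lower than Kaplan-Meier figures from older studies, so comparison with them is less direct unless the supplement is kept.
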